#### **Secondary Objectives Outcomes:**

- Mean tumor volume change evaluated by pituitary MRI between baseline and weeks 4, 12, 24, 48, 72, and 96.
- Percent tumor volume change evaluated by pituitary MRI between baseline and weeks 4, 12, 24, 48, 72, and 96.
- Proportion of patients reaching tumor volume decrease of at least ≥ 20% after 4, 12, 48, 72, and 96 treatment weeks.
- Time to treatment response for treatment responders, defined as the time from the first injection to the first evaluation in which the patient reached a tumor volume decrease of at least ≥ 20%.
- Change in the grading score for disease-related symptoms between baseline and weeks 4, 12, 24, 48, 72, and 96.
- Incidence of pituitary hormone dysfunction on baseline and weeks 4, 12, 24, 48, 72, and 96.
- Proportion of patients reaching alpha subunit decrease of at least 50% on weeks 4, 12, 24, 48, 72, and 96.
- Proportion of patients reaching alpha subunit normalization on weeks 4, 12, 24, 48, 72, and 96.
- Percentage of adverse events with CTC grade ≥ 3 during treatment with pasireotide LAR.
- Percentage of patients with at least one adverse event with CTC grade ≥ 3.
- Incidence of all adverse events, incidence of abnormal laboratory values, and summary of laboratory evaluations.
- For the extension phase: among patients considered as responders (i.e., patients reaching a tumor volume decrease of at least 20% compared to the initial tumor volume), evaluate the number and proportion of patients remaining responsive throughout the extension phase treatment period (according to magnetic resonance imaging evaluations on weeks 48, 72, and 96).
- To evaluate the percentage of patients remaining with stable tumor volume throughout the study, i.e., patients mantaining a tumor volume variation of less than 20% in relation to baseline tumor volume (according to magnetic resonance imaging evaluations on weeks 24, 48, 72, and 96).

Study design	A Phase II, open-label, single-arm, prospective, multicenter study to evaluate the efficacy and safety of pasireotide LAR 60 mg in adult patients with NFPA.				
	Main Phase: During the main phase of the study, visits will be performed every 28 ± 3 days, with 2 extra safety visits on days 20 and 76. For all evaluations and visits of the Main Phase, see Table 7-1.				

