#### 3.2.1 Secondary objective endpoints

The secondary variables are:

- Mean change in tumor volume evaluated by pituitary MRI between baseline and weeks 4, 12, 24, 48, 72, and 96.
- Percent change in tumor volume evaluated by pituitary MRI between baseline and weeks 4, 12, 24, 48, 72, and 96.
- Proportion of patients reaching tumor volume decrease of at least  $\geq$  20% after 4, 12, 48, 72, and 96 weeks of treatment.

- Time to treatment response for treatment responders, defined as the time from the date of the first injection to the first evaluation in which the patient reached a tumor volume decrease of at least ≥ 20%.
- Change in grading score of disease-related symptoms between baseline and weeks 4, 12, 24, 48, 72, and 96.
- Incidence of pituitary hormone dysfunction at baseline and on weeks 4, 12, 24, 48, 72, and 96.
- Proportion of patients reaching alpha subunit decrease of at least 50% on weeks 4, 12, 24, 48, 72, and 96.
- Proportion of patients reaching alpha subunit normalization on weeks 4, 12, 24, 48, 72, and 96.
- Percentage of adverse events with CTC grade  $\geq 3$  during treatment with pasireotide LAR.
- Percentage of patients with at least one adverse event with CTC grade  $\geq 3$ .
- Incidence of all adverse events, incidence of abnormal lab values, and summary of laboratory evaluations.
- For the extension phase: among patients who had been considered as responders (i.e., patients reaching a tumor volume decrease of at least 20% compared to initial tumor volume), to evaluate the number and proportion of patients who remained responsive during the extension phase treatment (according to the magnetic resonance imaging evaluations on weeks 48, 72, and 96).
- To evaluate the percentage of patients remaining with stable tumor volume during the study, i.e., patients who mantained tumor volume variation lower than 20% compared to baseline tumor volume (according to magnetic resonance imaging evaluations on weeks 24, 48, 72, and 96).
- If applicable, to evaluate whether there was a difference in response among patients on 40 and 60 mg doses of pasireotide LAR.

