1.2 SECONDARY OBJECTIVES

- To assess the effect of pasireotide LAR on the mean change of tumor volume from baseline to Week 4, 12, 24, 48, 72 and 96.
- To assess the effect of pasireotide LAR on the percentage change of tumor volume from baseline to Week 4, 12, 24, 48, 72 and 96.
- To assess the effect of pasireotide LAR on the proportion of patients achieving tumor volume reduction of at least ≥20% after 4 and 12, 48, 72 and 96 weeks of treatment.
- To assess the effect of pasireotide LAR on the time to tumor response.
- To assess the effect of pasireotide LAR on the disease-related symptoms*
 - *Disease-related symptoms to be evaluated: headache, visual disturbances, fatigue, decreased libido, erectile dysfunction (for males only), irregular or stopped menses (for not post-menopausal female only).
- To evaluate the effect of pasireotide LAR on pituitary function at Weeks 4, 12, 24, 48, 72 and 96.
- To evaluate the effect of pasireotide LAR on alpha subunit levels at Weeks 4, 12, 24, 48, 72 and 96.
- To evaluate the overall safety and tolerability of pasireotide LAR.
- For extension phase: duration of response for patients considered responsive (*i.e.*, patients who achieved a tumor volume reduction of at least 20% with respect the initial tumor volume).
- To assess the percentage of patients that remain with tumor volume stable during the study.

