1.2.1 End-points for secondary objectives

The secondary variables are:

Mean change of tumor volume assessed by pituitary MRI from baseline to Week 4, 12, 24, 48, 72 and
 96.

- Percent change of tumor volume assessed by pituitary MRI from baseline to Week 4, 12, 24, 48, 72 and
 96.
- Proportion of patients achieving tumor volume reduction of at least ≥ 20% after 4, 12, 48, 72 and 96 weeks of treatment.
- Time to treatment response for treatment responders, defined as the time from the date of first injection to the first evaluation the patient achieves tumor volume reduction of at least >20%.
- Change from baseline to Week 4, 12, 24, 48, 72 and 96 in disease-related symptoms scores.
- Incidence of pituitary hormonal dysfunction at baseline and at Weeks 4, 12, 24, 48, 72 and 96.
- Proportion of patients achieving alpha subunit reduction of at least 50% at Weeks 4, 12, 24, 48, 72 and 96.
- Proportion of patients achieving normalization of alpha subunit at Weeks 4, 12, 24, 48, 72 and 96.
- Percentage of CTC (≥3) adverse events during treatment with pasireotide LAR.
- Percentage of patients with at least one adverse event with CTC grade ≥ 3.
- Incidence of all adverse events, incidence of laboratory abnormal values and summary of laboratory assessments.
- For extension phase: among patients who had been considered as responsive (*i.e.*, patients who achieved a reduction in tumor volume of at least 20% with respect to the initial tumor volume), assess the number and proportion of patients that remained responsive during the treatment period of extension phase (according to estimates by magnetic resonance at weeks 48, 72 and 96).
- To assess the percentage of patients who remained with tumor volume stable during the study, *i.e.* patients who maintained tumor volume with variation less than 20% with respect to the basal tumor volume (according to evaluations by magnetic resonance imaging at weeks 24, 48, 72 and 96).
- If applicable, assessing whether there was difference in response between patients using dose of 40 and 60 mg of pasireotide LAR.

2 Study design

This is a prospective, multicenter, open-label, single arm, phase II study to evaluate the efficacy and safety of pasireotide LAR in adult patients with NFPA.

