For the Core Period of the study, efficacy and safety analyses will be conducted on the data collected by the time when all the enrolled patients have completed their EOS Visit. All the formal safety follow-up data of those patients who did not enter the extension study will also be included in the core study safety analyses. A final analysis will be completed when all the patients in the Extension complete their last visit and will be reported in either an additional clinical study report or in an addendum to the core study report.

Other additional data prior to the end of the Core Phase of the trial will be analyzed and then summarized in an additional report of clinical study or in a major study report.

Novartis or designated CRO will analyze all data using the SAS System for data analysis 9.4 . Any data analyses carried out independently by an investigator should be submitted to Novartis before publication or presentation.

The data from all centers participating in the trial will be combined, so that an adequate number of patients will be available for analysis. The statistical analysis methods described in this section will focus on the analysis of the data in the core study. Similar methods will be applied to the analyses in the Extension Phase as appropriate.

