of at least 20% with respect to the initial tumor volume				
in the core phase				
≥20% tumor volume reduction ^{c)} , n (%)				
Yes				
No				
Total				
For patients who achieved a reduction in tumor volume				
$$ $\!$ $\!$ $\!$ $\!$ $\!$ $\!$ $\!$ $\!$ $\!$ $\!$				
phase				
≥20% tumor volume reduction ^{c)} , n (%)				
Yes				
No				
Total				

a) The difference between visit i and V1.

b) For reduction='yes' will be considered all patients who obtained 'volume in visit i – volume in V1' >0.
c) For reduction ≥20%='yes' will be considered all patients who obtained 'Percentage change in volume at visit i' ≥20.

Table R 5 - Disease-related symptoms - FAS population

	Total					
	(n=xx) V13	V16	V19	V22	V25	V28
Headache, n (%)						
Absent						
Mild						
Moderate						
Severe						
Very severe						
Total						
mproved, n (%)						
Yes						
No						
Total						
Visual disturbances, n (%)						
Absent						
Mild						
Moderate						
Severe						
Very severe						
Total						
mproved, n (%)						
Yes						
No						
Total						
Fatigue, n (%)						
Absent						
Mild						
Moderate						
Severe						
Very severe						
Total						
mproved, n (%)						
Yes						
No Tatal						
Total						
Erectile dysfunction, n (%)						
Yes						
No						
Total						

Improved, n (%)

Yes

No

Total

Regular menses, n (%)

Yes

No

Total

Improved, n (%)

Yes

No

Total

a) For each symptom, it will considered as improvement if the severity reduce at least one point (eg. 'Severe' at v1 and 'moderate' at v1 will be considered as improvement in vi).

b) For patients who registered 'No' in V_1 and 'Yes' in v_i it will be considered as an improvement in v_i . c) For patients who registered 'No' in V_1 and 'Yes' in v_i it will be considered as an improvement in v_i .

Total (n=xx)	Table B 6 – Alpha-su	ubunit – FAS popula	ation		
α subunit (ng/mL) - N - Mean - Median - Standard Deviation - Minimum - Maximum - Normal - Abnormal - CS - NCS - Reduction of α subunit ≥50% ^{b)} , n (%) Yes - No - Total -					
N Mean		V16	V22	V28	
N Mean					
N Mean					
N Mean					
N Mean					
N Mean					
N Mean					
N Mean					
N Mean					
N Mean					
N Mean					
N Mean					
N Mean					
N Mean					
Mean - Median - Standard Deviation - Minimum - Maximum - Normal - Abnormal - CS - NCS - Reduction of α subunit ≥50%b), n (%) - Yes - No - Total -	N SUBURIT (ng/mL)		-		
Standard Deviation Minimum Maximum Normal Abnormal CS NCS Reduction of α subunit ≥50%b), n (%) Yes No Total	Mean		-		

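### The extension durability endpoint (core responders who remained responsive over Weeks 48, 72 and 96) has no planned output: Table B 4 counts response visit by visit, which gives only an upper bound

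*SAP*

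**What the plan says.** **The endpoint.** SAP 1.2.1 asks the analyst, among responders, to "assess the number and proportion of patients that remained responsive during the treatment period of extension phase". The judgement rests on the three extension MRIs, at Weeks 48, 72 and 96. Protocol 3.2.1 agrees: "to evaluate the number and proportion of patients who remained responsive during the extension phase treatment". The Protocol synopsis is more explicit about time: "evaluate the number and proportion of patients remaining responsive throughout the extension phase treatment period". The parent objective in SAP 1.2 is "For extension phase: duration of response for patients considered responsive".

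**The planned output.** Table B 4 in SAP Appendix 2 has columns V16, V22 and V28, which are Weeks 48, 72 and 96 in SAP Table A 2. For patients who had, in the core phase, a reduction "of at least 20% with respect to the initial tumor volume", it offers Yes, No and Total in each column. Footnote c) gives the scoring rule: "For reduction ≥20%='yes' will be considered all patients who obtained 'Percentage change in volume at visit i' ≥20". A further subgroup block follows. Its header is not legible in the text reviewed, so nothing here rests on it, but its row carries the same footnote.

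**The methods text.** SAP 5.5.1 contains no durability analysis. For the extension, SAP section 5 says only: "Similar methods will be applied to the analyses in the Extension Phase as appropriate".

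**The concern.** The endpoint is one number built from each responder's sequence of three scans. The table gives three cross-sections. A responder who drops below 20% at Week 72 and recovers by Week 96 is a Yes in two of the three columns, and nothing in the table shows that response was interrupted.

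The core phase supplies no method to carry over. Its time-to-response analysis (SAP 5.5.1 and Table 8) concerns when response begins, not whether it lasts. Table B 4 is the only Appendix 2 table on tumour volume.

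At stake is the only planned measure of how long response holds, a purpose for which the extension was added. If the shell is followed, either the endpoint goes unreported or a per-visit percentage stands in for it. If a rule is chosen at analysis, it is chosen with a handful of responders already in view.

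**Working it through.** **Size of the responder group.** The documents give no figure for this endpoint. The nearest is in SAP 5.6: the chance of two or more responders among 19 at a true rate of 10%.

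- P(X ≥ 2) = 1 − 0.9^19 − 19 × 0.1 × 0.9^18 = 1 − 0.1351 − 0.2852 = 0.580. The stated 58% is reproduced.
- SAP Table A 4 tabulates 2 to 6 responders of 19. I use that range for R, the number of core responders.

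**What the per-visit counts imply.** Assume complete data, reductions correctly coded, and the same count *a* of Yes at each of the three visits.

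- Each visit has R − a patients scored No, so at most 3(R − a) different patients are ever No. At least R − 3(R − a) = 3a − 2R are Yes throughout.
- A patient who is Yes throughout is Yes at each visit, so the sustained count is at most *a*.
- Hence max(0, 3a − 2R) ≤ sustained ≤ a.

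| R | a at each visit | Per visit | Sustained count | Sustained % |
|---|---|---|---|---|
| 2 | 1 | 50% | 0 to 1 | 0 to 50% |
| 3 | 2 | 67% | 0 to 2 | 0 to 67% |
| 4 | 3 | 75% | 1 to 3 | 25 to 75% |
| 5 | 4 | 80% | 2 to 4 | 40 to 80% |
| 6 | 5 | 83% | 3 to 5 | 50 to 83% |

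If a = R, both figures are 100%.

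Take R = 4. Patterns YYY, NYY, YNY and YYN give 3/4 in every column and 1/4 sustained. Patterns YYY, YYY, YYY and NNN also give 3/4 in every column, but 3/4 sustained. Table B 4 would look the same in both cases.

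**Direction when scans are missing.** SAP 5.4.3 analyses observed data, so per-visit denominators can shrink. With dropout as the only cause of missing scans, a responder has 8 + 4 + 2 + 1 = 15 possible patterns. Four responders give C(18, 4) = 3,060 combinations.

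- Sustained count over all core responders: no observed per-visit proportion was below it in any combination. The reason is simple: the Yes count at a visit is at least the sustained count, and its denominator is at most R.
- Sustained count over patients with all three MRIs: at least one per-visit proportion was below it in 231 of 3,060. For example, three patients YYY and one Yes, No, missing give 4/4, 3/4 and 3/3 per visit. Sustained is 3/3 among completers and 3/4 among all four.

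**A coding point met on the way.** Footnote a) takes change as visit i minus V1. Footnote b) calls a positive difference a reduction, and footnote c) requires a value of at least 20. Read to the letter, a tumour that shrank by 25% has a change of −25 and is scored No. The bounds above assume that this sign is put right.

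**The case against.** A reader might infer that the per-visit figures always overstate durability. The documents do not support that. They equal the sustained figure when the same patients respond each time, and with a completer denominator the order can reverse. Only the upper-bound statement, on a fixed core-responder denominator, stands.

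A reader might also take response at all three MRIs as the rule the documents already lay down. Only the Protocol synopsis speaks of the whole period. Protocol 3.2.1 and SAP 1.2.1 are looser, and no text says that one scan below 20% ends response. Protocol 7.5.7 attributes changes under 20% possibly to measurement artefact, and Protocol 6.4.5.1 asks for a second MRI before growth is accepted. A tumour truly stable a little beyond a 20% reduction could fail an all-three rule through scan error alone, so that rule may sit below true durability. This stands. It is a reason to show each responder's scans beside the summary, not to leave the summary out.

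The remaining argument is scale: a descriptive secondary endpoint in a proof-of-concept trial, with perhaps 2 to 6 responders and possibly fewer entering the extension. A listing would settle the matter, and the SAP's similar-methods sentence would permit an extra row. That lowers the importance. But no responder listing is specified for the extension, and permission to add a row does not say what goes in it.

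**Conclusion.** The point holds in a limited form. The number and proportion of core responders who remained responsive over the three extension MRIs is a stated secondary endpoint, and no planned table, row or rule produces it.

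The readable core-responder block of Table B 4 bounds it from above on a fixed core-responder denominator. With complete data the gap can be nil or large: 80% at every visit is compatible with 40% to 80% sustained, and 75% with 25% to 75%. These are logical limits, not predictions. They rest on equal counts at each visit and on reductions being coded as reductions.

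The primary endpoint is not affected by this gap. The change is worth making before the extension analysis because the group is so small: with 2 to 6 responders, one patient moves the result by 50 (1/2) to 17 (1/6) percentage points, so the rule should be written first.

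**What to change.** In SAP 5.5.1 and Table B 4:

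1. Add one patient-level row for core responders: remained responsive is Yes if the reduction from V1 is at least 20% at each of V16, V22 and V28. Report n/N with an exact CI.
2. State what makes a core responder: response at Week 24, or at any core MRI.
3. State the denominator: all core responders, or only those entering the extension.
4. State how a missing MRI is counted, and how a patient is counted who stops before Week 96 while still responsive. Protocol section 4 allows treatment to end for reasons such as commercial availability.
5. List, for each responder, the percent change at every MRI and the first MRI with a reduction under 20%, so that single-scan dips are visible.
6. Keep the per-visit rows, labelled as cross-sectional.
7. Correct the sign in footnotes b) and c). Table 7 in Appendix 1 carries the same notes.

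The cost is one derived variable, one row and a short listing from MRI data already planned. The downside is slightly more programming and a durability figure that may be lower than the per-visit percentages.
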